#### **2.5.4.2 Secondary Outcome Measures**

##### Secondary outcomes:

Non-compartmental modeling to determine plasma PK parameters of ondansetron – i.e. volume of distribution (Vd), clearance (CL), maximum CSF and plasma concentration (Cmax), and the time to reach these maximum concentrations (Tmax).

Compartmental modeling using population PK approach to determine CSF pharmacokinetic parameters of ondansetron.

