## 1. SYNOPSIS

Study Title	Investigation of cerebrospinal fluid (CSF) pharmacokinetics of ondansetron
Brief Title	CSF PK of ondansetron
Objective	To determine human cerebrospinal fluid (CSF) and plasma pharmacokinetic parameters of 5HT3R antagonist ondansetron after intravenous administration.
Hypothesis	Approaches to enhance CNS penetration of ondansetron might be useful for obtaining analgesic effect with 5HT3R antagonists in neuropathic pain.
Study Period	Planned enrollment duration: Approximately 3 months Planned study duration: One (4-hour) study day per subject, on the day of knee/hip arthroplasty surgery.
Number of Subjects	15 evaluable subjects having elective hip or knee arthroplasty with spinal anesthesia from up to 30 consented subjects.
Study Treatment	Single intravenous 15-min infusion of 16mg ondansetron.
Study Design	Prospective, open-label, pharmacokinetic pilot study.
Inclusion and Exclusion Criteria	
Inclusion criteria:
 
 
1. Age between 18 and 70 years old;
 
2. Patients planned to undergo hip or knee arthroplasty with spinal anesthesia;
 
3. Ability to provide informed consent
 
 
Exclusion criteria:
 
 
4. Not giving consent to participate in the study;
 
5. Patients with history of or current hepatic or renal insufficiency;
 
6. Patients with <math>BMI \geq 33</math>;
 
7. Patients with heart failure or active arrhythmias;
 
8. Patients with severe systemic disease that is a constant threat to life;
 
9. Contraindication or allergy to ondansetron;
 
10. Pregnancy or lactation.
 
11. Prisoners
 

Measurements	
Ondansetron CSF and plasma Pharmacokinetics:
 
 
1. A single 4-mL CSF sample per subject.
 
2. Serial blood sampling at 0 (pre-infusion), 15, 30, 60, 120, and 180 min after ondansetron administration.
 
 
Genotyping: A blood sample will be obtained at baseline for determining the following single nucleotide polymorphisms (SNPs) as confounders of ondansetron PK parameters:
 
 
1. ABCB1 gene (p-Glycoprotein transporter): C3435T, G2677T, T-129C, G1199A, C1236T.
 

	2. In SLC22A1 gene (OCT1 transporter): R61C, C88R, G401S, M420del, G456R.

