Statistical Methodology	
This is a pilot/feasibility study. Individual plasma concentration-time data will be analyzed using non-compartmental methods in Phoenix WinNonlin® 6.1, to determine ondansetron PK parameters such as volume of distribution (Vd), clearance (CL), maximum plasma concentration (Cmax), and the time to reach maximum concentration (Tmax).
 
A compartmental population-based PK model will be constructed, to determine the pharmacokinetic variables of ondansetron in CSF, and allow for the estimation of the partition coefficient between the plasma and CSF.

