## 2.5 Design and Procedures

### 2.5.1 Study Design and Methodology

The potential subjects will be recruited from the Washington University / Barnes Jewish Hospital center for perioperative assessment and planning (CPAP) and the Washington University Orthopedics outpatient clinics, before their scheduled visit for elective knee or hip arthroplasty. Subjects may also be recruited from BJH Surgery Registration and the preoperative holding area on the day of surgery. Subjects who are potential candidates for the study will be provided with written and oral description of the study procedures, benefits, and potential risks. They will be given the opportunity to ask questions regarding the study. Informed consent will take place at Washington University/Barnes-Jewish Hospital medical center campus.

If agreeing to participate in the study, each subject will sign the informed consent document. Each subject who qualifies for entry into the study on the basis of inclusion/exclusion criteria and completion of informed consent will be assigned the next available patient number. This indicates enrollment in the study. In subjects with a history of or suspected renal or hepatic disorder, blood tests will be ordered following consent and reviewed prior to study participation for plasma creatinine, Alanine aminotransferase (ALT), Aspartate aminotransferase (AST) and albumin. Subjects with moderate or severe renal or hepatic failure will be excluded from the study at the discretion of the PI. Subjects with any history of cardiac arrhythmias will undergo 12 lead ECG to rule out QTc interval >450ms and will be excluded from the study.

Patients' demographic data will be recorded; height and weight will be measured for calculating BMI. Subjects who drop out of the study prior to completing the study will be replaced by using the next available subject number.

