### 2.5.2 Study Period

Subjects will be studied in the Department of Anesthesiology of Washington University-Barnes Jewish Hospital, prior to and during their scheduled hip or knee arthroplasty surgery.

An intravenous catheter will be inserted in an arm for drug administration and in the opposite arm for obtaining blood samples to evaluate the plasma concentrations of ondansetron. The former will be used also for pre/intraoperative fluids and anesthesia drug administration.

At baseline, a 5ml blood sample will be collected for pharmacokinetics and another 5ml sample for genetic analysis.

Ondansetron will be administered in a 16mg single dose as a 15 min intravenous infusion. Although up to 32mg doses of intravenous ondansetron have been used in clinical trials, 16mg is currently the highest FDA-recommended dose for single administration. Two additional 4mg doses of either IV or oral ondansetron will be allowed for postoperative nausea and vomiting treatment in the study subjects, at the discretion of the treating physicians.

A single CSF sample of 4ml will be collected immediately after spinal needle insertion and before administration of spinal anesthesia. This procedure is routinely performed in the holding area, approximately 30 min before the patient enters the operating room (OR) for planned surgical procedure with spinal anesthesia. As only one sample of CSF is obtained from each subject, the timing of the infusion will be scheduled at approximately 30, 60, or 120 min before planned pre-surgical spinal needle insertion. This will allow 3 time-points of CSF samples from the aggregate study cohort. For determination of the above timing, the patients will be randomized in blocks of 3 for infusion timing (approximately 5 subjects per block), to allow even distribution of CSF PK sample time-points.

Six 5mL serial venous blood samples will be obtained from all subjects at 0 (pre-treatment), 15, 30, 60, 120, and 180 min from the beginning of infusion in each patient, regardless of timing for CSF sampling. The samples will be put on ice, centrifuged for 10 min at 5000 rpm. Plasma will be transferred to two 1.5mL vials and stored at -80°C until analysis by HPLC-MS.

The CSF ondansetron pharmacokinetic profile will be constructed using population PK approach, according to the exact time of CSF sampling. Ondansetron concentration in plasma (expected 40-120ng/mL) and CSF (expected 3-12ng/ml) will be determined by HPLC-MS-MS analysis [10].

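### Section 2.5.4.2 places CSF Cmax and CSF Tmax under non-compartmental analysis, which one CSF sample per subject at a randomised time cannot support

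*Combined protocol and SAP*

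**What the plan says.** The first secondary outcome in section 2.5.4.2 is non-compartmental modelling. It opens by limiting itself to plasma parameters, but its list then includes "maximum CSF and plasma concentration (Cmax), and the time to reach these maximum concentrations (Tmax". The plural at the end takes in CSF Tmax as well as CSF Cmax. The second secondary outcome, on the next line, reads "Compartmental modeling using population PK approach to determine CSF pharmacokinetic parameters of ondansetron".

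On sampling, the Synopsis (Measurements) specifies "A single 4-mL CSF sample per subject". Section 2.5.2 explains how the sampling time is set: "the timing of the infusion will be scheduled at approximately 30, 60, or 120 min before planned pre-surgical spinal needle insertion", with the interval assigned by randomisation. Plasma is sampled six times in every subject.

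On analysis, the Synopsis (Statistical Methodology) names only "maximum plasma concentration (Cmax), and the time to reach maximum concentration (Tmax" under the non-compartmental method, and for CSF says "A compartmental population-based PK model will be constructed, to determine the pharmacokinetic variables of ondansetron in CSF". Section 2.5.2 agrees: "The CSF ondansetron pharmacokinetic profile will be constructed using population PK approach, according to the exact time of CSF sampling". Section 2.5.4.3 applies non-compartmental methods to each individual's plasma data, and cites the single CSF sample per patient as a case for which the population approach is well suited.

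**The concern.** A non-compartmental Cmax is the largest observed concentration in a profile, and Tmax is the time at which it was observed. Both need several samples from the same profile. Here the individual CSF profile is one point, and the design chooses its time. Taken literally, the outcome would report the sampling schedule as CSF Tmax, and a concentration at an assigned time as CSF Cmax. Differences between subjects in that Cmax would partly reflect the interval each was randomised to.

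The study exists to describe CSF pharmacokinetics, and section 2.1 says the results are to support a later study of enhanced CNS penetration. A CSF Tmax fixed by the schedule would misinform that study. Section 2.5.4.2 is also the only place where a CSF peak and its timing are named as outcomes, so anyone reporting from the outcome list would find them attached to the wrong method.

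**Working it through.** **Inputs from the documents.** 15 evaluable subjects (Synopsis; 2.4); 1 CSF sample per subject (Synopsis; 2.5.2); nominal intervals of 30, 60 and 120 min, randomised (2.5.2); 6 plasma samples per subject (2.5.2).

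**The plan's own figure.** Section 2.5.2 expects approximately 5 subjects, which I read as the number per timing. 15 / 3 = 5, so it is reproduced.

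**Data available.**
- CSF: 15 × 1 = 15 values, one per subject.
- Plasma: 15 × 6 = 90 values, six per subject.

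**What individual non-compartmental analysis returns for CSF.** With one observation (t, C), Cmax = C and Tmax = t. Assume actual times equal nominal times and the clock runs from the start of infusion. With 5/5/5 subjects at 30/60/120 min:
- mean = (5×30 + 5×60 + 5×120)/15 = 1050/15 = 70 min
- median = 60 min (the 8th of 15 ordered values)
- SD = √{[5×(−40)² + 5×(−10)² + 5×50²]/14} = √(21000/14) = 38.7 min

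No property of the drug enters these figures.

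**Dependence on the allocation.** Section 2.5.1 says dropouts "will be replaced by using the next available subject number", and the final split could be uneven. Two illustrative splits, not taken from the documents:

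| Subjects at 30/60/120 min | Mean Tmax | Median | SD |
|---|---|---|---|
| 5/5/5 | 70 | 60 | 38.7 |
| 6/5/4 | (180+300+480)/15 = 64 | 60 | 37.4 |
| 4/5/6 | (120+300+720)/15 = 76 | 60 | 39.1 |

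The mean moves by 6 min in either direction with the drug unchanged. If the intervals run from the end of the 15-min infusion and Tmax from its start, 15 min is added to every value: for 5/5/5 the mean is 85, the median 75 and the SD still 38.7 min. Real sampling times would scatter around the nominal ones.

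**How far this could lie from the true peak (illustration only).** Assumptions not in the documents: one-compartment plasma kinetics with a 4 h half-life, a 15-min infusion, and a CSF compartment following dCe/dt = ke(Cp − Ce), with ke = ln 2 / equilibration half-life.

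| Assumed equilibration half-life (min) | True CSF Tmax (min) | C/Cmax at 30 min | at 60 min | at 120 min |
|---|---|---|---|---|
| 10 | 56 | 0.86 | 1.00 | 0.87 |
| 30 | 110 | 0.53 | 0.86 | 1.00 |
| 60 | 167 | 0.35 | 0.67 | 0.95 |
| 120 | 247 | 0.24 | 0.48 | 0.80 |

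The true Tmax ranges from 56 to 247 min across these assumptions, while the tabulated non-compartmental Tmax would be the same in every row. In the last two rows the peak falls after the last nominal CSF sample.

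**Consistency of the text.** Two places (Synopsis, 2.5.4.3) describe non-compartmental analysis as being of individual plasma data. Four places (Synopsis, 2.5.2, second item of 2.5.4.2, 2.5.4.3) give CSF pharmacokinetics to the population model. Only the first item of 2.5.4.2 departs from this, and it also contradicts its own opening restriction to plasma.

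**The case against.** The strongest reply is that these are stray words in a sentence whose stated scope is plasma, and that the operative analysis text already handles CSF correctly. On that view nobody planned a CSF non-compartmental analysis, so the Tmax figures describe something that would not happen. Much of this stands: the likely explanation is a drafting slip, and the practical harm is limited. But the plasma restriction at the start makes the sentence contradict itself; it does not settle which part governs. The entry is also in the outcome list, not in background text.

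A second reply is that a pooled, sparse-sampling non-compartmental analysis could give one CSF Cmax and Tmax for the cohort, since section 2.5.2 refers to three time-points across the whole group. That is technically possible, but the documents plan no such analysis, and at nominal times its Tmax could only be 30, 60 or 120 min.

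A third reply is that deletion alone would cure the contradiction, and that model-based peak predictions go further than the plan requires: the only specific CSF quantity named for the model is the plasma–CSF partition coefficient. This is fair, and deletion is an acceptable remedy.

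**Conclusion.** The point holds: the first item of section 2.5.4.2 is wrong as written. It ties two CSF quantities to a method that cannot estimate them from one sample per subject, and it conflicts with the rest of the plan's text on CSF pharmacokinetic parameters. Followed literally, it would yield a CSF Tmax with mean 70, median 60 and SD 38.7 min by design. Those figures assume 15 evaluable subjects split 5/5/5, nominal sampling times and a clock started at the beginning of infusion; the conclusion itself does not depend on them.

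The severity is low. The primary outcome in 2.5.4.1 uses measured concentrations and the CSF-to-plasma ratio and is untouched. So are the plasma Cmax and Tmax and the planned population model. It should still be corrected, because the contradiction is clear and the correction costs almost nothing.

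**What to change.** In section 2.5.4.2, restrict the non-compartmental item to plasma: Vd, CL, plasma Cmax and plasma Tmax. Then choose one of two courses for CSF.

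- **Keep them as outcomes.** List CSF Cmax and CSF Tmax under the population PK item, defined as predictions from the fitted population CSF curve and reported with an uncertainty interval. State that if the fitted peak falls after the last CSF sample, the report will say that the peak was not reached within the sampled window.
- **Drop them.** Delete the CSF wording from the non-compartmental item and leave the general CSF parameters with the population model.

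Dropping them costs one reworded sentence. Keeping them also means deriving the predictions and intervals from the model already planned. Neither needs new samples, subjects or procedures. The drawback of keeping them is that peak predictions based on 15 CSF values may be imprecise, and the interval would show this.

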#### **2.5.4.3 Pharmacokinetic data analysis:**

Individual plasma concentration-time data will be analyzed using non-compartmental methods. The following PK parameters will be calculated and compared between subjects with different transporter expression level: volume of distribution, systemic clearance, the elimination half-life, and the total area under the concentration-time curve. In addition, a compartmental population-based pharmacokinetic model will be constructed, which will evaluate inter-subject variability in pharmacokinetic parameters. Preliminary assessment of published data indicates that the systemic disposition of ondansetron follows two-compartment model with linear elimination following intravenous administration in humans.

The population model will include a “CSF distribution compartment”, which will allow for the estimation of the partition coefficient between the plasma and CSF. The effect of transporter expression level phenotypes on individual pharmacokinetic parameters will be evaluated using a standard covariate analysis. Utilization of population approach will allow for estimation of population mean and individual patients parameters. This pharmacokinetic methodology is especially useful for analysis of sparse data (i.e., a single CSF sample from each patient).

### **2.5.5 Sample Size**

We plan to recruit 15 subjects to the current study, and propose additional enrollment of 60-80 patients to the subsequent study, upon securing sufficient extramural funding

Typically, 10-15 subjects per study have been used for the assessment of drug pharmacokinetic parameters and is sufficient for a pilot study.

Weekly, more than 30 total hip or knee arthroplasties with spinal anesthesia are performed at our institution. This corresponds to approximately 1000 eligible patients a year that may fulfill the inclusion criteria.

### **2.5.6 Study design considerations**

. A large number of patients undergo total joint arthroplasty at our institution, and spinal anesthesia is standard care; therefore, it will be possible to recruit patients who meet the inclusion criteria without the added risk of spinal needle insertion. Ondansetron is routinely administered in these patients for the prophylaxis or treatment of postoperative nausea and vomiting.

The dose of 16mg ondansetron was chosen, as this is currently the highest recommended dose by FDA for a single administration and was shown safe among patients between ages 18-75. Intravenous 15-minute infusion is chosen over bolus administration to reduce QTc prolongation risks. We did not choose lower doses to be able to reliably measure CSF concentrations, as sampling volume is typically limited to about 4mL, to reduce the risk of post spinal headache. The timing of CSF sampling was based on intravenous ondansetron PK data [17].

### **2.5.7 Clinical Procedures and Laboratory Tests**

Due to the risk of QT interval prolongation with high doses of ondansetron, we exclude patients with QTc > 450ms, and any concomitant administration of drugs that increase the pro-arrhythmic risk with ondansetron. In addition, all subjects will be monitored with ECG for potential arrhythmias. However, it should be noted that ondansetron administration is standard of care in these patients. Blood hepatic function and renal tests will be performed and evaluated prior to study treatment for any subjects with suspected or known kidney and or liver disease.

## **3.0 Management of Intercurrent Events**

### **3.1 Adverse Experiences**

The investigators will closely monitor subjects for evidence of ondansetron adverse events. All adverse events will be reported and followed until satisfactory resolution. The description of the adverse experience will include the time of onset, duration, severity, etiology, relationship to the study drug (none, unlikely, possible, probable, highly probable), and any treatment required. The clinicians will manage any postoperative event related to the spinal anesthesia as standard of care.

### **3.2 Premature Discontinuation**

If a subject withdraws from the study, the subject will be replaced in order to provide the required number of evaluable subjects. Subjects will be withdrawn if the investigator decides that discontinuation is in the best interest of the subject, or the subject requests withdrawal from the study.

### **3.3 Potential Risks**

#### **3.3.1 Potential risks from ondansetron**

Ondansetron systemic effects associated with high plasma concentration may cause cardiac arrhythmias.

In addition, subjects may experience diarrhea, constipation, headache, dry mouth, malaise, elevation of liver enzymes (incidence of 5% - when administered with chemotherapy to treat nausea and vomiting), and injection site reaction.

Rarely reported adverse effects include:

Hypokalemia, Fever, Anaphylaxis, Seizures, Temporary blindness.

However, this dose is used frequently for postoperative or chemotherapy-induced nausea and vomiting, and is considered safe. In previous studies with 16mg intravenous ondansetron administration, no patient had arrhythmias or other serious side effects; headache and malaise were the main adverse effects [8, 9]. No psychological risks to subjects are envisioned.

### **3.3.2 Other Potential Risks**

Intravenous catheter placement can cause a bruise. The amount of blood drawn is approximately 35cc and will not constitute a risk to subjects since this amount is well below the recommended limits for this population. Spinous catheter placement is a part of the routine perioperative care in this patient group; therefore there is no additional risk as a result of study participation. The collection of a 4mL CSF sample will be performed by an anesthesiologist immediately following spinal needle insertion for standard of care anesthesia. This additional collection of CSF is not expected to increase the risk of post-dural puncture headache, but it may occur, especially in younger patients. No psychological risks to subjects are envisioned. Subjects may experience a loss of confidentiality. Investigators will keep subjects' participation confidential to the extent permitted by law. However, it is possible that others may become aware of subjects' participation in this study and may inspect and copy records pertaining to this research. Some of these records could contain information that personally identifies subjects. The results of genotyping will not result in identifiable, clinically diagnostic genetic information that has a known association with a medical condition. The data from the analysis will not be included in the patients' medical records.

### **3.4 Procedures to Minimize Potential Risks**

Studies are conducted in the Washington University Clinical Research Center under the supervision of the PI and Co-investigators. The PI is trained and experienced in performing research in human subjects, and the co-investigators are board-certified anesthesiologists with extensive clinical and research experience in the perioperative setting.

Subjects are also continuously monitored by trained research (RN) nursing personnel throughout the study session and by their clinical team during surgery and recovery in the Post Anesthesia Care Unit (PACU), as a part of routine care. Subjects will be monitored by electrocardiogram for any potential cardiac abnormalities associated with ondansetron administration. Full patient monitoring and resuscitation capabilities are immediately available.

The 16mg dose of ondansetron, when infused over 15 minutes in adults 18-74 years old, was shown not to increase the QTc interval by more than 10ms, even if additional two doses of 8mg are administered later in the day [18]. Based on these data, and the current FDA recommendation, we will administer 16mg dose by 15-min infusion, and apply an upper age limit of 70 years on the study population.

Inclusion and exclusion criteria, monitoring, and the clinical protocol are designed to ensure that risks are absolutely minimal. Subjects are informed that participation is voluntary and they may refuse to participate and may withdraw from the study at any time without penalty. A pregnancy test will be performed on women of childbearing potential and subjects excluded if pregnant. Subjects will be told that in the event of a physical injury as the direct result of study procedures, they will be cared for by a member of the investigating team at no cost, within the limits of the Washington University compensation plan.

With regard to confidentiality; 1) all subjects will be assigned a study ID number, 2) Samples will be kept confidentially. They will be coded, with a key to the code linking code numbers to names kept at a separate location, under lock and key. 3) The link to identifiers will be destroyed at the end of the study. 4) Data will be stored under lock and key (office, file cabinet) and only the investigators and research team will have access. If data are published, there will be no link to identifiers. Study data will not be revealed to any organization, individuals other than the subjects, or the subjects themselves. 5) Study data will not be entered in subjects' medical records.

